10.5 Primary analyses

The recruitment rate (defined as the number of recruited participants divided by the number of eligible participants), will be estimated along with a 95% CI. The number of participants recruited will be presented by site, as will the overall average number of participants recruited per site per month.

The trial retention will be measured at the end of the 8-month study follow-up. For each outcome, an estimate of the attrition rate (the number of forms not returned divided by the number of forms due) will be produced along with a 95% confidence interval. This will be done for the study overall and by group (treatment vs control).

Intervention adherence will be measured at the 14 week follow up. Adherence will be expressed as a percentage with a maximum of 100% attendance reflecting 7 out of 7 treatment sessions attended for CMT and 5/5 attended for PiP. The total number and percentage of participants attending >66% of CMT sessions and 100% of PiP F2F sessions.

These summaries will be used to assess success of the trial against the pre-specified progression criteria.

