4.2 Secondary objectives

This trial will examine, and aims to gain insight into, the following secondary objectives:

- Can sufficient numbers of study participants be recruited and retained to enable an RCT? (feasibility trial)
- What is the physiotherapist acceptability of the intervention? (qualitative evaluation)
- What is the patient acceptability of the intervention? (feasibility trial via adherence, and qualitative evaluation)
- What is the suitability of various outcome measures for use in an RCT? (feasibility trial)

The following stop-go criteria will be monitored to indicate overall trial feasibility.

1 Recruitment: Average participants recruited per month: red: <4 per month; amber: 4-6 per month; green> 6 per month.

2: Adherence/retention: Participants attending >5 (of 7) clinical sessions: <60%; amber=60-79%; green \geq 80%.

3: Outcomes: Participants providing 14-week and 6 month data: red<60%; amber=60-79%; green \geq 80%. Appropriateness of outcomes determine via qualitative evaluation.

4 Acceptability to patients. Determined via the qualitative evaluation.

5. Outcomes

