5.3.2 Trial retention

The proportion of withdrawals and the proportion of completed 6-month questionnaires will be used to determine trial retention. Withdrawals and losses to follow up will be classified as:

- Participant withdrawn from follow-up only
- Participant withdrawn from the intervention but agrees to further follow-up
- Participants fully withdrawn from the intervention and follow up
- Participants lost to follow-up
- Participant has died

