Appendix A: Baseline table

Table 1. Baseline demographics and outcome measures of randomised participants, both as randomised and for those completing the 8-month timepoint assessments

Characteristics	As randomised			Followed up at 6 months		
	Intervention (n=x)	Control (n=x)	Overall (n=)	Intervention (n=x)	Control (n=x)	Overall (n=)
Age, years						
N, mean (SD)						
Gender, n (%)						
Male						
Female						
Trans						
BMI						
N, mean (SD)						
Outcome measures, N, mean (SD)						

Neck Disability Index						
NRS						
PCS-H subscale						
PCS-M subscale						
PCS-R subscale						
PCS total score						
Tampa scale						
START MSK						
EQ-5D-5L index value score						
EQ-5D-5L VAS						

Table 2. Diversity and inclusion demographics

Age	Intervention (n=x)	Control (n=x)	Overall (n=x)
Up to and including 24 years			
25-34 years			
35-44 years			
45-54 years			
55-64 years			
65- 74 years			
75+ years			
Prefer not to say			
Disability	Intervention	Control	Overall
Yes			
No			
Prefer not to say			
Yes – substantial barriers or limitations			
Yes – some/small barriers or limitations			
No			
Ethnicity	Intervention	Control	Overall
Bangladeshi			
Chinese			
Indian			
Pakistani			

Any other Asian background (please describe below)			
Black / African / Caribbean / Black British			
African			
Caribbean			
Any other Black / African / Caribbean background (please describe below)			
White			
English / Welsh / Scottish / Northern Irish / British			
Gypsy or Irish Traveller			
Irish			
Roma			
Any other white background (please describe below)			
Arab			
Hispanic			
Latina/Latino/Latinx			
Any other ethnic group			
Religion	Intervention	Control	Overall
No religion			
Bhuddist			
Christian			
Hindu			
Jewish			
Muslim			
Sikh			
Spiritual			
I have a religion or strongly held belief but prefer not to specify what this is			
Prefer not to say			
Any other religion or belief (please describe below)			
Socio-economic background	Intervention	Control	Overall
Modern professional & traditional professional occupations such as: teacher, nurse, physiotherapist, social worker, musician, police officer (sergeant or above), software designer, accountant, solicitor, medical practitioner, scientist, civil / mechanical engineer			
Senior, middle or junior managers or administrators such as: finance manager, chief executive, large business owner, office manager, retail manager, bank manager, restaurant manager, warehouse manager			

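### The recruitment and retention summaries in SAP 10.5 are not the quantities on which stop-go criteria 1 and 3 are set, and 10.5 times retention at 8 months in a trial whose last assessment is at 6

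*SAP*

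**What the plan says.** **The criteria (SAP 4.2).** Criterion 1 is "Average participants recruited per month: red: <4 per month; amber: 4-6 per month; green> 6 per month". Criterion 3 is set on "Participants providing 14-week and 6 month data", with red below 60%, amber 60-79% and green at 80% or more.

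**The analysis (SAP 10.5).** The recruitment rate is recruited over eligible participants, with a 95% CI. Counts are given by site, together with the "overall average number of participants recruited per site per month". For retention: "The trial retention will be measured at the end of the 8-month study follow-up". Attrition is then estimated for each outcome, overall and by group, as "the number of forms not returned divided by the number of forms due". The section closes by saying that these summaries are what the progression criteria will be judged on.

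**Other places.** Section 5.3.2 says that the proportion of withdrawals and "the proportion of completed 6-month questionnaires will be used to determine trial retention". The Follow-up paragraph after 5.3.7, and sections 7.1, 10.3 and 10.8, give baseline, 14 weeks and 6 months as the assessment times. Section 5.3.5 gives a 6-month period for adverse events. The only other mention of 8 months is the Appendix A Table 1 title, which refers to "those completing the 8-month timepoint assessments"; that table's own column head says 6 months. Section 10.3 plans a graph of monthly recruitment for the whole trial and a log of collected and analysable data at each timepoint.

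**The concern.** Section 5.1 makes recruitment, retention and adherence the primary outcomes, and 10.5 is their analysis section. A threshold can only be applied to the quantity on which it was set. For criteria 1 and 3 the analysis section stops short of that quantity, so someone has to choose the bridging calculation once the data are in. The choices are the counting period, the handling of sites, which outcome's form counts, and whether one visit or both are required. Some of these can move a result across a colour boundary. The 8-month timing adds a plain contradiction to the definition of a primary outcome. What is at stake is a progression decision that two competent analysts could reach differently from the same data.

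**Working it through.** **1. The plan's own figure.** Inputs from section 7 (Sample Size): 48 participants, 20% dropout. 48/2 × (1 − 0.20) = 19.2 per group, which reproduces the stated figure of about 19.

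**2. Criterion 1 against 10.5.**

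| | Unit |
|---|---|
| Criterion 1 | participants per month, whole trial |
| 10.5, first summary | recruited / eligible |
| 10.5, second summary | participants per site per month |
| 10.3 | monthly recruitment, as a graph |

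*Recruited over eligible* contains no time. Recruiting 48 in 6, 8, 12 or 16 months (assumed durations) gives 48/6 = 8, 48/8 = 6, 48/12 = 4 or 48/16 = 3 per month: green, amber, amber, red. The ratio of recruited to eligible could be the same in all four cases.

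*Per site per month* must be scaled by the number of sites, which the SAP does not state. An assumed 1.5 per site per month becomes 3.0, 4.5, 6.0 or 7.5 for the trial with 2, 3, 4 or 5 sites: red, amber, amber, green. Scaling also fails when sites open at different times. Assumed example: 24 recruited in 12 months at one site and 24 in 6 months at another.

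- Whole trial: 48/12 = 4.0 per month.
- Mean of site rates: (24/12 + 24/6)/2 = 3.0; times 2 sites = 6.0 per month.

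Both happen to be amber, but they sit at opposite ends of the band.

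**3. Criterion 3 against 10.5.** The criterion counts participants; 10.5 counts forms, separately for each outcome. Section 5.2 lists six questionnaires, so there are at least six attrition rates for the trial overall, and 10.5 does not say which is set against 60% and 80%.

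If the criterion requires both visits, form return at each visit does not determine it. With m of N returning at each visit, the number with both lies between max(0, 2m − N) and m. Assume m = 41, N = 48:

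- Each visit: 41/48 = 85.4%, attrition 14.6%.
- Lower bound for both: 2 × 41 − 48 = 34; 34/48 = 70.8%, amber. This needs the 7 missing at one visit to be entirely different people from the 7 missing at the other.
- Upper bound: 41/48 = 85.4%, green. This arises when the same 7 are missing at both visits.
- Independent visits: (41/48)² = 73.0%, amber.

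If the criterion judges each visit separately, the range disappears and 1 minus attrition for a given form is close to the criterion. The wording of criterion 3 allows either reading.

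**4. Timing.** Sections 5.3.2, 5.3.5, 7.1, 10.3 and 10.8 and the Follow-up paragraph all stop at 6 months. Against them stand one sentence in 10.5 and one table title, which its own column head contradicts. No form is due at 8 months.

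**5. Bands (minor).** Amber ends at 79% and green starts at 80%. 38/48 = 79.2% lies between them unless percentages are rounded to whole numbers, and the SAP gives no rounding rule. Criterion 2 uses the same bands.

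**The case against.** The best defence is that nothing is missing from the data. Section 10.3 plans the trial-wide monthly recruitment graph and the per-timepoint log, so both criteria can be worked out from what is already kept. That is correct, and it is why this is a gap in definition and cross-reference rather than an unmeasured outcome. It does not remove the point: 10.5 names its own summaries as the basis for the decision, and a graph is not an estimate with a stated counting period.

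Four stronger readings are tempting, and the SAP does not support them.

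- A reader might infer that the plan would call a green trial red, since 7 per month is 7/2 = 3.5 per site with 2 sites and 7/3 = 2.3 with 3. That requires an assumed number of sites, and an analyst who sets a figure labelled per site against a threshold that is not. It is a possible misreading, not a prescribed error.
- A reader might infer that 85% form return really means about 73% retention. That takes the joint reading of criterion 3 as settled and assumes independence between visits. If loss is mainly dropout, those who return 6-month forms are largely those who returned 14-week forms, and the joint share is near 85%.
- A reader might infer that the 8-month sentence will produce a wrong retention result. With no form due at 8 months, no rival value could be computed; the effect is an unclear definition.
- A reader might infer that planned retention falls in the gap between bands. The planning value is 80%, which is green; 79.2% appears only after 19.2 per group is rounded to 19, and whole-percent rounding would make it amber.

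**Conclusion.** The point holds as a mismatch of definitions. For criterion 1, neither recruitment summary in 10.5 fixes the colour. For criterion 3, the unit is wrong (forms per outcome instead of participants), the rate to be compared is not named, and the stated timing contradicts the rest of the SAP. These conclusions rest on the text alone. The figures for durations, sites and 41 of 48 rest on assumed inputs; they show that the colour can depend on an unstated choice, not that it will be wrong. The 70.8% to 85.4% range applies only under the joint reading. The gap between the bands is minor. Overall this is a should-fix: it concerns the primary feasibility outcomes and the progression decision, but the data are already planned and the remedy is wording.

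**What to change.** In SAP 10.5:

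1. **Criterion 1.** Compute total participants recruited divided by months of recruitment for the whole trial, and state when counting starts and ends. Keep recruited over eligible and the per-site rates as descriptive summaries.
2. **Criterion 3.** Compute the number of randomised participants providing data divided by all randomised, with a 95% CI. State whether 14-week and 6-month data are required jointly or judged separately, and which form or forms count as providing data. The authors should make that choice openly, since the joint reading is the stricter one. Keep per-outcome attrition as supporting information.
3. **Timing.** Replace 8-month with 6-month in 10.5 and in the Appendix A Table 1 title.
4. **Minor, in 4.2.** Write amber as 60% to <80% for criteria 2 and 3, so that 38/48 has a defined colour without relying on rounding.

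The cost is an SAP wording amendment. No new data are needed, because 10.3 already covers the inputs. It should be made before outcome data are examined, so that the go/no-go metric is not chosen with the results in view.

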10.6 Intervention fidelity

Intervention fidelity scores will be summarised (Appendix D).

10.7 Adverse events

Adverse events and serious adverse events will be presented by trial arm and site, itemised with descriptions (Appendix E).

10.8 Health Economics

We will be collecting patients' response to EQ-5D-5L instrument and patient-reported questionnaire on health resource utilisation at baseline, 14 weeks and 6 months as part of the health economic evaluation. All data will be summarised descriptively by group and follow-up time points.

The feasibility of undertaking an economic evaluation of the CMT intervention versus control group will be the primary objective of the health economic analysis. Of note, a full economic evaluation will not be conducted. Instead, an economic evaluation framework will be established to assess the feasibility of data collection methods being used in this study and help identify the appropriate instruments for the collection of relevant health economics data in order to inform full economic evaluation of the future pragmatic RCT.

The distribution of participants' response to the five dimensions of EQ-5D-5L instrument and utility will be tabulated at baseline, 14 weeks and 6 months. QALYs of each participant at each follow-up time points and total QALYs will be generated with the "area under curve" (trapezoidal) method by assuming linear interpolation between measurements over time. In accordance with NICE's position statement, patients' responses to the EQ-5D-5L questionnaire will be mapped to EQ-5D-3L to derive the health utility of patients at each follow-up time point.

An NHS and Personal Social Services (PSS) perspective will be adopted for the analysis of health care resource utilisations, which means all health care-related resources used by the

patients that are reimbursed by NHS will be considered. Health care utilisation data at each follow-up time point will be collected and presented for relevant resources used by patients in primary care, community (i.e. appointments with a GP, nurse, physiotherapist, occupational therapist, and other primary/community care healthcare professionals) and hospital setting (i.e. hospital outpatient attendances, accident and emergency admissions, day case attendances and inpatient admissions). Participants will be asked to record their resource use specifically in relation to neck pain and whether the appointment/contact was face-to-face or remote (phone/online). Mean resource use by cost category will be summarised, and completion rates will be presented. Considering that this is a feasibility trial and full economic evaluation was deemed unnecessary, unit costs for the healthcare resources will not be attached to the units of resource utilisations to derive the total costs.

Missing EQ-5D-5L and resource utilisation data will be inspected to understand the likely mechanism of missingness to help guide appropriate imputation methods to deal with the missing data.

As full economic evaluation is not necessary, the common issues around trial-based economic evaluation such as baseline imbalances, correlated costs and effects, and skewness of costs and effects will not be considered in our study. The sampling uncertainty will not be considered as well and as a result, non-parametric bootstrapping will also not be applied.

9. SAP amendment log

Amendment/addition to SAP and reason for change	New version number, name and date
Draft	V1.0
Draft	V2.0
Signed version	V3.0

10. Signatures of approval

Sign-off of the final approved version of the Statistical Analysis Plan by the principle investigator and trial statistician(s) (can also include Trial Manager/Co-ordinator)

Name	Trial Role	Signature	Date

11. References

Appendix A: Baseline table

Table 1. Baseline demographics and outcome measures of randomised participants, both as randomised and for those completing the 8-month timepoint assessments

Characteristics	As randomised			Followed up at 6 months		
	Intervention (n=x)	Control (n=x)	Overall (n=)	Intervention (n=x)	Control (n=x)	Overall (n=)
Age, years						
N, mean (SD)						
Gender, n (%)						
Male						
Female						
Trans						
BMI						
N, mean (SD)						
Outcome measures, N, mean (SD)						

Neck Disability Index						
NRS						
PCS-H subscale						
PCS-M subscale						
PCS-R subscale						
PCS total score						
Tampa scale						
START MSK						
EQ-5D-5L index value score						
EQ-5D-5L VAS						

Table 2. Diversity and inclusion demographics

Age	Intervention (n=x)	Control (n=x)	Overall (n=x)
Up to and including 24 years			
25-34 years			
35-44 years			
45-54 years			
55-64 years			
65- 74 years			
75+ years			
Prefer not to say			
Disability	Intervention	Control	Overall
Yes			
No			
Prefer not to say			
Yes – substantial barriers or limitations			
Yes – some/small barriers or limitations			
No			
Ethnicity	Intervention	Control	Overall
Bangladeshi			
Chinese			
Indian			
Pakistani			

Any other Asian background (please describe below)			
Black / African / Caribbean / Black British			
African			
Caribbean			
Any other Black / African / Caribbean background (please describe below)			
White			
English / Welsh / Scottish / Northern Irish / British			
Gypsy or Irish Traveller			
Irish			
Roma			
Any other white background (please describe below)			
Arab			
Hispanic			
Latina/Latino/Latinx			
Any other ethnic group			
Religion	Intervention	Control	Overall
No religion			
Bhuddist			
Christian			
Hindu			
Jewish			
Muslim			
Sikh			
Spiritual			
I have a religion or strongly held belief but prefer not to specify what this is			
Prefer not to say			
Any other religion or belief (please describe below)			
Socio-economic background	Intervention	Control	Overall
Modern professional & traditional professional occupations such as: teacher, nurse, physiotherapist, social worker, musician, police officer (sergeant or above), software designer, accountant, solicitor, medical practitioner, scientist, civil / mechanical engineer			
Senior, middle or junior managers or administrators such as: finance manager, chief executive, large business owner, office manager, retail manager, bank manager, restaurant manager, warehouse manager			

Clerical and intermediate occupations such as: secretary, personal assistant, call centre agent, clerical worker, nursery nurse			
Technical and craft occupations such as: motor mechanic, plumber, printer, electrician, gardener, train driver			
Routine, semi-routine manual and service occupations such as: postal worker, machine operative, security guard, caretaker, farm worker, catering assistant, sales assistant, HGV driver, cleaner, porter, packer, labourer, waiter/waitress, bar staff			
Long-term unemployed (claimed Jobseeker's Allowance or earlier unemployment benefit for more than a year)			
Small business owners who employed less than 25 people such as: corner shop owners, small plumbing companies, retail shop owner, single restaurant or cafe owner, taxi owner, garage owner			
Other (for example unemployed due to disability)			
Prefer not to say			

Table 3- Patient reported experience measure

Characteristics	As randomised			Followed up at 6 months		
	Intervention (n=x)	Control (n=x)	Overall (n=)	Intervention (n=x)	Control (n=x)	Overall (n=)
MSK PREM						

Appendix B: COMPIN CONSORT DIAGRAM

<https://testlivesalfordac.sharepoint.com/sites/BEPKO298/Shared%20Documents/General/Trial%20-%20COMPIN/Ethics%20and%20recruitment/Recruitment%20and%20screening/COMPIN%20CONSORT%20diagram.docx>

Appendix C: Recruitment and retention summary tables

Table 2: Recruitment log

Site	Number Identified and sent PIS by CRN	Number contacted and screened (95% CI)	Number Consenting (95% CI)	Number Randomised (95% CI)	Number Withdrawn (95% CI)
Total					

Table 3: Withdrawal's log

Site	Participant ID	Reason for Withdrawal

Table 4: Summary of outcomes by treatment group and time point

Continuous outcome measures, N, mean (SD)	14 weeks			6 months		
	Intervention (n=x)	Control (n=x)	Overall (n=)	Intervention (n=x)	Control (n=x)	Overall (n=)
WOMAC Pain subscale						
PCS-H subscale						

PCS-M subscale						
PCS-R subscale						
PCS total score						
Tampa scale						
EQ-5D-5L index value score						
EQ-5D-5L VAS						
Categorical outcome measures, n (%)						
PCS total score ≥ 30						
Tampa scale >37						
Severe (20- 24)						

Appendix D: Notes audit log

Appendix E: Adverse events

ID	Description	Severity	Action taken	Outcome	Allocation

Adverse events	Intervention	Control	Total

	(N =)	(N =)	(N =)
Serious Adverse Events N (%)			
Relatedness			
Related			
Unrelated			
Expectedness			
Expected			
Unexpected			
Non-Serious Adverse Events N (%)			
Grading			
Mild			
Moderate			
Severe			
Relatedness			
Related			
Unrelated			
Expectedness			
Expected			
Unexpected
